5 STUDY POPULATION

5.1 INCLUSION CRITERIA

Individuals must fulfil all of the following criteria to be eligible for inclusion in this trial:

Demography

1. Male or female (non-pregnant, non-lactating) aged 18 to 55 years inclusive who will be contactable and available for the duration of the trial and up to two weeks following the EOS visit.
2. Total body weight greater than or equal to 50 kg, and a body mass index (BMI) within the range of 18 to 32 kg/m² (inclusive). BMI is an estimate of body weight adjusted for height. It is calculated by dividing the weight in kilograms by the square of the height in metres.

Health status

3. Certified as healthy by a comprehensive clinical assessment (detailed medical history and full physical examination).
4. Fully vaccinated (meaning first, second and booster dose) against COVID-19 within 14 days of planned inoculation date.
5. Vital signs at screening (measured after 5 min in the supine position):
 - Systolic blood pressure (SBP) - 90–140 mmHg,
 - Diastolic blood pressure (DBP) - 40–90 mmHg,
 - Heart rate (HR) 40–100 bpm.
6. At Screening and pre-inoculation with the malaria challenge agent: normal standard mean of triplicate 12-lead electrocardiogram (ECG) parameters after 5 minutes resting in supine position in the following ranges:
 - a. *QTcF ≤450 msec (male participants); QTcF ≤470 msec (female participants);*
 - b. *QRS 50–120 msec*
 - c. *PR interval ≤ 210 msec for both males and females, and*
 - d. *Normal ECG tracing unless the PI or delegate considers an ECG tracing abnormality to be not clinically relevant.*
7. Women of childbearing potential (WOCBP) who anticipate being sexually active with a male during the trial must agree to the use of a highly effective method of birth control (see below) combined with a barrier contraceptive from the screening visit until 100 days after the last dose of pyronaridine (covering a full menstrual cycle of 30 days starting after 5 half-lives of last dose pyronaridine) and have a negative result on urine pregnancy test performed before inoculation with the malaria challenge agent.

Note:

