Laboratory abnormalities will be presented as cross-tabulations of the abnormality at each post-treatment baseline analysis visit versus the treatment baseline. Numbers of participants with treatment-emergent abnormalities will also be shown.

In addition, the liver function tests, namely AST, ALT, and total bilirubin, are used to assess possible drug-induced liver toxicity. The proportion of patients with Potential Clinically Significant Abnormality (PCSA) values at any post base line visit will summarized. The highest value of PCSA and time to the highest PCSA reading will also be summarized. Any of the following event will be considered as a PCSA:

- Any ALT or AST value above 5×ULN.
- An elevation in bilirubin 2×ULN.
- Any AST or ALT value above 2×ULN and (total bilirubin >1.5×ULN).
- Any AST or ALT value above 2×ULN with the appearance of fatigue, nausea, vomiting, right upper quadrant pain or tenderness, fever, rash and/or eosinophilia (eosinophil percent or count above the ULN).
- Constitutes a possible Hy's Law case
 - Hy's Law case is defined as a Participant with any value of alanine or aspartate aminotransferase greater than 3×ULN together with an increase in total bilirubin to a value greater than 2×ULN and not associated to an alkaline phosphatase value greater than 2×ULN (FDA Guidance on Drug Induced Liver Injury: Premarketing Clinical Evaluation [2009]).

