11.4 Vital Signs

Parameters

- Systolic Blood Pressure (SBP) (mmHg)
- Diastolic Blood Pressure (DBP) (mmHg)
- Heart Rate (beats/minute)
- Temperature (°C)
- Respiratory rate (beats/min)

Biostatistical methods

All vital signs data will be listed for all participants. Any values outside of the protocol defined normal ranges will be flagged, with clinical significance status presented for out-of-range results.

Table 2: Vital Signs Normal Ranges

Parameter	Range
Systolic blood pressure	90-140 mmHg
Diastolic blood pressure	50-90 mmHg
Heart rate	50-100 bpm
Temperature	35.0-37.5°C
Respiratory rate	10-25 breaths/min

Vital sign parameters will be summarised by presenting summary statistics for observed values and change from treatment baseline values for each scheduled visit.

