11.5 Body Measurements

Definition of variables

- Height (Screening Only)
- Weight

- Body mass index (BMI)

Biostatistical methods

Body measurement data will be listed for all participants and visits including height, weight and Body Mass Index (BMI) which is auto-calculated within the CRF.

Observed values, as well as changes from treatment baseline, will be summarised descriptively for weight and BMI by visit.

Physical Examination

Parameters

• Weight• HEENT (Head, Eyes, Ears, Nose, Throat)• Height (screening only)• Chest / Lungs• Abdomen	
• Skin• Neurological / Reflexes• Heart / circulation• Neck
---	---

Biostatistical methods

Physical examination findings will be listed for all participants and visits

11.6 12-lead ECG

Parameters

- PR interval (msec)
- QRS interval (msec)
- QTcF interval (msec)
- Overall ECG assessment (Normal, Abnormal, Not Evaluable)
- ECG abnormality (as appropriate)
- Clinical Significance

Biostatistical methods

ECG parameters will be listed for all participants and visits. Triplicate ECGs will be presented in listings for individual readings as well as the mean for each triplicate. The triplicate means will be used for the summary table. Any values outside of the protocol defined normal ranges (Table XX) will be flagged.

Table 3: ECG Normal Ranges

Parameter	Range
PR interval	≤210 msec
QRS	50–120 msec
QTcF	Males: ≤450 msec Females: ≤470 msec

Observed values, as well as changes from treatment baseline, will be summarised descriptively for all ECG parameters by visit. An addition table will present the frequencies of participants who fulfill the following prolongation (change from baseline) criteria, considering all scheduled and non-scheduled visit data:

- QTcF prolongation >30
- QTcF prolongation >60
- QTcF >450 msec for males
- QTcF >470 msec for females
-

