Overall Summary of Treatment Emergent Adverse Events	IMP
Summary of Inoculum Emergent Adverse Events by MedDRA System Organ Class and Preferred Term	FAS
Summary of Treatment Emergent Adverse Events by MedDRA System Organ Class and Preferred Term	IMP
Summary of Inoculum Emergent Adverse Events by Maximum Severity	FAS
Summary of Treatment Emergent Adverse Events by Maximum Severity	IMP
Summary of Inoculum related Treatment Emergent Adverse Events by MedDRA System Organ Class, Preferred Term	FAS
Summary of IMP Related Treatment Emergent Adverse Events by MedDRA System Organ Class, Preferred Term	IMP
Summary of Inoculum Related IAEs by System Organ Class, Preferred Term and Maximum Severity	FAS
Summary of IMP Related TEAEs by System Organ Class, Preferred Term and Maximum Severity	IMP

Inoculum Emergent Serious Adverse Events by MedDRA System Organ Class and Preferred Term	FAS
Treatment Emergent Serious Adverse Events by MedDRA System Organ Class and Preferred Term	IMP
Overall Summary of Inoculum Emergent Adverse Events of Special Interest (AESI)	FAS
Overall Summary of Treatment Emergent Adverse Events of Special Interest (AESI)	IMP
Inoculum Emergent Adverse Events of Special Interest (AESI) by MedDRA System Organ Class and Preferred Term	FAS
Treatment Emergent Adverse Events of Special Interest (AESI) by MedDRA System Organ Class and Preferred Term	IMP
Summary of Concomitant Medications (FAS)	FAS
Summary of Concomitant Medications (IMP)	IMP
Haematology (Summary and Change from IMP Baseline)	FAS
Haematology (Categorical)	FAS
Cross-Tabulation of Haematology Abnormalities Versus IMP Baseline	FAS
Biochemistry (Summary and Change from IMP Baseline)	FAS
Biochemistry (Categorical)	FAS
Cross-Tabulation of Biochemistry Abnormalities Versus IMP Baseline	FAS
Liver Function: Summary of Participant Potentially Clinically Significant Abnormality	FAS
Liver Function: Summary of Peak Readings Since IMP Administration	FAS
Liver Function: Summary of Time to Peak Readings Since IMP Administration in Days	FAS
Urinalysis (Categorical)	FAS
Vital Signs Results and Change from IMP Baseline	FAS
Abnormal Vital Signs Results	FAS
ECG Results and Change from IMP Baseline	FAS
ECG QTc Categorical Analyses	FAS
ECG Clinical Assessment	FAS

MMV_PYR_21_01 SAP_V1.1_06Feb23

Final Audit Report

2023-02-17

Created:	2023-02-16 (Australian Central Standard Time (Northern Territory))
By:	[name] ([contact])
Status:	Signed
Transaction ID:	CBJCHBCAABAkV7vApbvRoRStFhB2QHJ3BrAw8SU8fhC

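### The QTcF prolongation table can count participants already above the limit before dosing, or never dosed, and heart-rate and diastolic floors lie inside the entry limits; neither table compares with treatment baseline as the laboratory tables do

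*SAP*

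**What the plan says.** **Entry limits** (Protocol 5.1, criteria 5 and 6). Vital signs at screening, supine: "Systolic blood pressure (SBP) - 90–140 mmHg", "Diastolic blood pressure (DBP) - 40–90 mmHg" and "Heart rate (HR) 40–100 bpm". QTcF, as the mean of triplicate ECGs at screening and before inoculation: at most 450 ms in men and 470 ms in women.

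**On-trial normal ranges** (Protocol 8.3.4 and 8.3.5, repeated in SAP 11.4 and 11.6). Systolic 90–140 mmHg, diastolic 50–90 mmHg, heart rate 50–100 bpm, QTcF at most 450/470 ms. On-trial vital signs are taken seated.

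**Vital-sign rule.** SAP 11.4 says of the listing: "Any values outside of the protocol defined normal ranges will be flagged, with clinical significance status presented for out-of-range results". It then describes summaries of observed values and of change from treatment baseline by scheduled visit. SAP Appendix Table B adds a table titled "Abnormal Vital Signs Results", on the FAS.

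**QTcF rule.** SAP 11.6 gives four rows under one label that calls them prolongation, in the sense of change from baseline: increase above 30, increase above 60, above 450 ms in men, and above 470 ms in women. They are counted "considering all scheduled and non-scheduled visit data". Table B puts this table on the FAS too. SAP 5.1.1 defines the FAS as everyone who received the challenge agent.

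**Comparison rule for laboratory data.** SAP 11.3.3: "Laboratory abnormalities will be presented as cross-tabulations of the abnormality at each post-treatment baseline analysis visit versus the treatment baseline". It also plans numbers of participants with treatment-emergent abnormalities.

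**The concern.** An abnormality count describes a drug's effect only if it separates what was present before the drug from what appeared after it. The absolute QTcF rows do not do this, although their label says they do. The vital-sign floors can classify a participant's ordinary state as abnormal.

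The trial has no placebo group, and the proposed Cohort 1 dose groups have two participants each, so one participant makes 50% of a dose-group column. Protocol 2.2.1 lists bradycardia among the frequent adverse events of the pyronaridine combination, and Protocol 8.5.3 makes QTcF above 480 ms an event of special interest. Readers will therefore look at exactly these rows.

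**Working it through.** No sample-size or power figure bears on this point, so there is no planned figure to reproduce. The check compares the limits, then the rules, then sizes the effect.

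**1. Limits side by side**

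| Measure | Entry | On trial | Relation |
|---|---|---|---|
| Systolic | 90–140 | 90–140 | equal |
| Diastolic | 40–90 | 50–90 | floor 10 inside entry |
| Heart rate | 40–100 | 50–100 | floor 10 inside entry |
| QTcF, men | ≤450 | ≤450 | equal |
| QTcF, women | ≤470 | ≤470 | equal |

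A usual heart rate or diastolic pressure of 40–49 is eligible and out of range at once. This needs no assumption about variability.

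**2. Who the absolute QTcF rows can count**

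- *Above the limit before dosing.* The Day 8 criteria (Protocol 7.1.1) list only QTcF above 480 ms. A man at 455 ms before dosing does not meet that criterion. If dosed, he is counted even if his QTcF then falls.
- *Never dosed.* A participant given rescue medication instead of pyronaridine on Day 8 stays in the FAS. With no post-dose limit, any value above 450/470 ms is counted.
- *Unscheduled pre-dose ECGs.* Protocol 5.4 allows unscheduled visits to follow up out-of-range ECGs during eligibility. On the literal wording these are also within the rows.

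**3. Chance of being counted with no drug effect, for a given true value**

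With p the chance that one reading is out of range and k independent readings, P(at least one) = 1 − (1 − p)^k. Readings after dosing, from Protocol 8.1.5, 8.1.6 and 8.1.8: vital signs k = 4×3 + 15 + 1 = 28; ECGs k = 4 + 15 + 1 = 20 (15 is about five outpatient weeks at three visits). The documents give no within-person SDs, so those below are assumptions. Readings are rounded to whole units.

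- Heart rate, true 45, SD 6: p = Φ((49.5 − 45)/6) = 0.773, and 1 − 0.227^28 ≈ 100%.
- Heart rate, true 60, SD 4 to 8: p = 0.004 to 0.095, giving 11% to 94%.
- Male QTcF, true 440, SD 8: p = 1 − Φ((450.5 − 440)/8) = 0.095, and 1 − 0.905^20 = 86%. With SD 5 to 10 the range is 30% to 96%.
- Male QTcF, true 420, SD 5 to 10: at most about 2%.

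**4. Chance across an assumed population**

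Participants were simulated with no drug effect, admitted on the entry limits, with independent noise. Assumed mean / between-person SD / within-person SD are shown. The any-reading column uses 13 to 30 readings.

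| Measure | Assumption | One reading | Any reading | Any reading, and baseline in range |
|---|---|---|---|---|
| Heart rate <50 | 64/9/6 | 9% | 33–42% | 25–33% |
| Systolic outside 90–140 | 120/10/7 | 4% | 23–33% | 20–29% |
| Diastolic outside 50–90 | 72/8/5 | 3% | 16–24% | 14–21% |

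Changing only the assumed mean heart rate to 72 gives 11–15% at any reading. With SDs of 8 and 4 as well, it gives 3–5%.

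For men's QTcF above 450 ms (mean 400–410, between-person SD 17, within-person SD 6–10, 6 to 20 ECGs) the rate is about 0.5% to 10%. If nine of 18 participants were men, the expected number is 9 × 0.005 to 9 × 0.10, or about 0.05 to 0.9.

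**5. Participants flagged at their usual value**

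If 5%, 10% or 20% of participants had a resting heart rate of 40–49 (assumed), the expected number of 18 is 0.9, 1.8 or 3.6. The chance of at least one is 1 − 0.95^18 = 60%, 1 − 0.90^18 = 85%, or 1 − 0.80^18 = 98%.

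**The case against.** The strongest reply is that SAP 11.4 describes a flag in a listing, not a count. The investigator's view of clinical significance stands beside each flag. The only tabulation described there is by scheduled visit, with change from treatment baseline, so someone enrolled at 45 bpm shows a change near zero. Protocol 9.4.4 likewise points to tables by scheduled visit. The abnormal vital-signs table is known only by its title. This stands: a reader might infer that a third or more of participants will be tabulated with abnormal heart rate at some visit, but the documents do not say that the table counts any visit, and that figure rests on assumed means and SDs.

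A reader might also infer that flagged values will become adverse events attributed to pyronaridine. The documents point the other way. Protocol 8.5.1 requires an abnormal assessment to be clinically significant and either new or worsened, and 8.5.3 excludes asymptomatic sinus bradycardia without other relevant ECG abnormalities from the events of special interest.

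For QTcF, rows for increases above 30 and above 60 sit in the same table, triplicate means are used where triplicates exist, and the label itself suggests post-baseline data. The Day 8 criteria are guidance, and the investigator may withhold dosing for other ECG signals. These points reduce the effect. They do not supply the missing condition, because the rule as written covers all visits on the FAS.

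Finally, entry vital signs are supine and on-trial ones seated, so the two ranges are not strictly like for like. An over-inclusive safety count is also defensible. Both points stand, and the second shapes the remedy.

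**Conclusion.** The point holds as a minor defect of specification in two descriptive safety tables. The primary PK/PD endpoint is untouched.

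Two parts need no assumed figures. The absolute QTcF rows carry a prolongation label but can count a participant above the limit before dosing or never dosed. An eligible participant with a usual heart rate or diastolic pressure of 40–49 is flagged without any change. Neither table is given the treatment-emergent comparison that the SAP gives laboratory data.

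The size is modest for QTcF: about 0.5–10% of men with no drug effect, under the assumptions shown. For vital signs no single rate can be defended. The any-reading figures assume independent readings and SDs that the documents do not give. Correlated readings would lower the chance for values near a limit, but would not help someone whose usual value is 40–49.

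It is tempting to conclude that requiring an in-range baseline would settle the matter. It would not. Heart-rate counts fall only from 33–42% to 25–33%, and for a man with true QTcF 440 ms and SD 8 the chance falls only from 86% to 78%, because most of the count is repeat-measurement noise. Such a rule would also hide a man dosed at 455 ms who rises to 475 ms, an increase of 20 ms.

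**What to change.** In SAP 11.4, 11.6 and Appendix Table B:

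1. Run the QTcF categorical table and the abnormal vital-signs table on the IMP Set, with post-dose data only.
2. Present each as IMP-baseline category by worst post-dose category, with a count of treatment-emergent abnormalities, as for laboratory data.
3. Keep the absolute QTcF counts above 450/470 ms, split by whether baseline was already above the limit, so that worsening from an abnormal baseline stays visible.
4. Label absolute rows and change rows separately, and add a row for QTcF above 450/470 ms together with an increase above 30 ms.
5. Leave every raw value, including pre-dose values and undosed participants, in the FAS listings.

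The shift layout shows each participant's starting category but does not remove repeat-measurement noise, so a footnote should say that the worst category depends on the number of readings. The limits themselves, eligibility and the Day 8 criteria are left alone. The cost is SAP wording and two revised table shells, with no new data.

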11.5 Body Measurements

Definition of variables

- Height (Screening Only)
- Weight

- Body mass index (BMI)

Biostatistical methods

Body measurement data will be listed for all participants and visits including height, weight and Body Mass Index (BMI) which is auto-calculated within the CRF.

Observed values, as well as changes from treatment baseline, will be summarised descriptively for weight and BMI by visit.

Physical Examination

Parameters

• Weight• HEENT (Head, Eyes, Ears, Nose, Throat)• Height (screening only)• Chest / Lungs• Abdomen	
• Skin• Neurological / Reflexes• Heart / circulation• Neck
---	---

Biostatistical methods

Physical examination findings will be listed for all participants and visits

11.6 12-lead ECG

Parameters

- PR interval (msec)
- QRS interval (msec)
- QTcF interval (msec)
- Overall ECG assessment (Normal, Abnormal, Not Evaluable)
- ECG abnormality (as appropriate)
- Clinical Significance

Biostatistical methods

ECG parameters will be listed for all participants and visits. Triplicate ECGs will be presented in listings for individual readings as well as the mean for each triplicate. The triplicate means will be used for the summary table. Any values outside of the protocol defined normal ranges (Table XX) will be flagged.

Table 3: ECG Normal Ranges

Parameter	Range
PR interval	≤210 msec
QRS	50–120 msec
QTcF	Males: ≤450 msec Females: ≤470 msec

Observed values, as well as changes from treatment baseline, will be summarised descriptively for all ECG parameters by visit. An addition table will present the frequencies of participants who fulfill the following prolongation (change from baseline) criteria, considering all scheduled and non-scheduled visit data:

- QTcF prolongation >30
- QTcF prolongation >60
- QTcF >450 msec for males
- QTcF >470 msec for females
-

11.7 Presentation of Safety Results

The table summary and listings of AEs and lab parameters will be presented for the CSR, and are provided in Appendix, Table B.

12. EXPLORATORY PARAMETERS

Not Applicable

13. CHANGES TO THE PLANNED ANALYSIS

There is no change to the planned analysis by the time when this SAP was written.

14. INTERIM AND FINAL ANALYSIS

This study has no formal interim analyses other than review of safety, tolerability, parasitaemia and PK parameters by the SDRT between cohorts.

15. SOFTWARE

SAS® Version 9.4 or higher (SAS Institute, Cary, North Carolina, USA) for Safety, demographic and baseline characteristics, volunteer disposition, protocol deviations, prior medications and treatment exposure analyses

All PK/PD analyses will be performed in R 4.1.3 and IQRtool package 1.10.0 [IQRtools]. NLME modelling will be performed with Monolix 2019R1 [MLX19] using Stochastic Approximation Expectation Maximization (SAEM) for parameter estimation. For PD modelling where typically the variance of random-effects cannot be estimated from the data, the IQRtools SysFit approach [KAS19] will be used to estimate typical and individual PD parameters.

Data manipulation and data analyses for all pharmacodynamic data will be performed using R (highest version available).

19. APPENDIX

Table A. PD and PK Planned Tables, Listings and Figures

Title	Analysis Set
PD Listings	
Pharmacodynamic –Parasitemia	PD
Pharmacodynamic –Parasite Life Cycle Stages	PD
PK Listings	
Pharmacokinetic Concentrations	PK
Pharmacokinetic Parameters	PK
PD Tables	
Summary of Pharmacodynamic in qPCR 18s	PD
Summary of Pharmacodynamic in Parasite Life Cycle Stages	PD
PK Tables	
Summary of Pharmacokinetic Concentration	PK
Summary of Pharmacokinetic Parameters	PK
PD Figures	
Individual qPCR 18s-time Profiles	PD
Individual RT-PCR pfs25-time Profiles	PD
Individual RT-PCR pfMGET-time Profiles	PD
Individual RT-PCR SBP-1-time Profiles	
PK Figures	
Arithmetic Mean (+SD) Pharmacokinetic Concentration-time Profiles	PK
Individual Pharmacokinetic Concentration-time Profiles	PK

Table B. Baseline Characteristics and Safety Analysis Tables and Listings

Title	Analysis Set
Listings	
Participant Disposition	FAS
Treatment Group Assignment	FAS
Protocol Deviations	FAS
Analysis Population Assignment	FAS
Demographics	FAS
Medical History	FAS
Beck Depression Index (BDI-2)	FAS
Pregnancy Test	FAS
Follicle Stimulating Hormone (FSH)	FAS
Serology Screening	FAS
Urine Drug Screening	FAS
Alcohol Breath Test	FAS
Prior and Concomitant Medications	FAS
Malaria Challenge Agent Administration	FAS
Study Drug Administration	FAS
Rescue Medication Administration	FAS
Inoculum-Emergent Adverse Events	FAS
Treatment-Emergent Adverse Events	IMP
Malaria Challenge Agent related Inoculum-Emergent Adverse Events	FAS
IMP related Treatment-Emergent Adverse Events	IMP
Inoculum Emergent Serious Adverse Events	FAS
Treatment Emergent Serious Adverse Events	IMP
Inoculum-Emergent Adverse Events Leading to Discontinuation	FAS
Treatment-Emergent Adverse Events Leading to Discontinuation	IMP

Inoculum-Emergent Adverse Events of Special Interest	FAS
Treatment-Emergent Adverse Events of Special Interest	IMP
Deaths	FAS
Individual Haematology Results	FAS
Individual Biochemistry Results	FAS
Coagulation Screening	FAS
Individual Abnormal Coagulation Results	FAS
Individual Urinalysis Results (dipstick)	FAS
Individual Urine Microscopy Results	FAS
Individual Vital Signs Results	FAS
Individual ECG Parameters Results	FAS
Physical Examination	FAS
Tables	
Analysis Populations	FAS
Participant Disposition	FAS
Demographics and Baseline Characteristics	FAS
Summary of Prior Medications	FAS
Protocol Deviations	FAS
Treatment Exposure	FAS
Overall Summary of Inoculum Emergent Adverse Events	FAS
Overall Summary of Treatment Emergent Adverse Events	IMP
Summary of Inoculum Emergent Adverse Events by MedDRA System Organ Class and Preferred Term	FAS
Summary of Treatment Emergent Adverse Events by MedDRA System Organ Class and Preferred Term	IMP
Summary of Inoculum Emergent Adverse Events by Maximum Severity	FAS
Summary of Treatment Emergent Adverse Events by Maximum Severity	IMP
Summary of Inoculum related Treatment Emergent Adverse Events by MedDRA System Organ Class, Preferred Term	FAS
Summary of IMP Related Treatment Emergent Adverse Events by MedDRA System Organ Class, Preferred Term	IMP
Summary of Inoculum Related IAEs by System Organ Class, Preferred Term and Maximum Severity	FAS
Summary of IMP Related TEAEs by System Organ Class, Preferred Term and Maximum Severity	IMP

Inoculum Emergent Serious Adverse Events by MedDRA System Organ Class and Preferred Term	FAS
Treatment Emergent Serious Adverse Events by MedDRA System Organ Class and Preferred Term	IMP
Overall Summary of Inoculum Emergent Adverse Events of Special Interest (AESI)	FAS
Overall Summary of Treatment Emergent Adverse Events of Special Interest (AESI)	IMP
Inoculum Emergent Adverse Events of Special Interest (AESI) by MedDRA System Organ Class and Preferred Term	FAS
Treatment Emergent Adverse Events of Special Interest (AESI) by MedDRA System Organ Class and Preferred Term	IMP
Summary of Concomitant Medications (FAS)	FAS
Summary of Concomitant Medications (IMP)	IMP
Haematology (Summary and Change from IMP Baseline)	FAS
Haematology (Categorical)	FAS
Cross-Tabulation of Haematology Abnormalities Versus IMP Baseline	FAS
Biochemistry (Summary and Change from IMP Baseline)	FAS
Biochemistry (Categorical)	FAS
Cross-Tabulation of Biochemistry Abnormalities Versus IMP Baseline	FAS
Liver Function: Summary of Participant Potentially Clinically Significant Abnormality	FAS
Liver Function: Summary of Peak Readings Since IMP Administration	FAS
Liver Function: Summary of Time to Peak Readings Since IMP Administration in Days	FAS
Urinalysis (Categorical)	FAS
Vital Signs Results and Change from IMP Baseline	FAS
Abnormal Vital Signs Results	FAS
ECG Results and Change from IMP Baseline	FAS
ECG QTc Categorical Analyses	FAS
ECG Clinical Assessment	FAS

MMV_PYR_21_01 SAP_V1.1_06Feb23

Final Audit Report

2023-02-17

Created:	2023-02-16 (Australian Central Standard Time (Northern Territory))
By:	[name] ([contact])
Status:	Signed
Transaction ID:	CBJCHBCAABAkV7vApbvRoRStFhB2QHJ3BrAw8SU8fhC

